In addition, a structured questionnaire will be used to obtain the estimated: i) time and material cost of installing the tool (feasibility) during installation, ii) perceived adverse effects after one month of installation, and iii) community acceptance of ITENs with ITWS. The physical durability of the intervention will be evaluated through physical inspection of the ITENs and ITWS for the continued presence and fabric integrity. Chemical durability will be assessed using samples of netting that will be evaluated for bioefficacy using laboratory reared populations of pyrethroid resistant *An. arabiensis*, *Culex quinquefasciatus*, *An. funestus* as well as pyrethroid susceptible *Aedes aegypti* mosquitoes, followed by chemical testing according to standard WHO guidelines and procedures (10). In addition, the perception, use and practice of the tool will be examined through Focus Group Discussions.

1 **Methods: Participants, interventions and outcomes**

2 **Study setting {9}**

3 The trial will be implemented in the villages of Pongwe, Madesa and Mazizi in Chalinze district
4 located in coastal Tanzania. The average rainfall is 1200 to 2100 mm per year and the average
5 temperature is approximately 28°C in the region. The region has two rainfall seasons yearly: the
6 long rainfall from March to May and short rainfall from November to December. The main
7 occupation for majority of the residents in villages of Chalinze is farming. The population of the
8 study area was 13,740 while the average household size in the district was 4.5 (11). The malaria
9 prevalence by PCR in the study area was more than 40% in the survey designed to assess
10 gametocyte in children of age 7 years old and above ([name]. *pers comm.*). More than sixty
11 percent of houses had window screens and thirteen percent had closed eaves in a study conducted
12 previously in the study area (11). An estimated 1800 people based on the average household size
13 and number of households will be tested for malaria at each survey, thus, nine hundred people per
14 arm will be screened for malaria.

15

16 **Eligibility criteria {10}**

17 Recruitment for the will be by household. To be eligible, residents must live in a house with strong
18 (intact) walls, having open eaves and unscreened windows. Residents of study houses who are
19 over the age of 6 months will be eligible for the follow up surveys.

20

21 **Eligibility criteria for individuals who will perform the interventions**

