2 the national guideline for treatment of uncomplicated malaria (13).

3

4 **Provisions for post-trial care {30}**

5 ITENs & ITWS will be installed in houses randomly selected in the negative control arm at the
6 end of the trial to ensure that all groups have access to the intervention.

7

8 **Outcomes {12}**

9 **Primary outcome**

10 Prevalence of malaria measured by qPCR shortly after long rainy season (June/July, year 2022) in
11 households with ITENs and ITWS installed in comparison to those without.

12 **Secondary outcomes**

13 - Prevalence of malaria measured by qPCR shortly after the short rainy season (January/
14 February 2022) in households with ITENs and ITWS installed in comparison to those without.

15 - Prevalence of clinical malaria cases (defined by axillary temperature of 37.5 degrees or above
16 and positive mRDT) shortly after the short rainy season (January/February 2022) and long
17 rainy season (June/July 2022) in households with ITENs and ITWS installed in comparison to
18 those without.

19 - Density of malaria vectors and nuisance mosquitoes present in houses with ITENs and ITWS
20 installed in comparison to the houses without after the short (January/February 2022) and long
21 (June/July 2022) rainy season measured by CDC light trap.

- 1 - The amount of fabric and time cost of installing ITENs and ITWS per house.
- 2 - The percentage of adverse effects among technicians and houses with ITENs and ITWS after
3 one month of installation.
- 4 - The physical presence and numbers of holes visually observed in ITENs and ITWs after 6
5 months and 12 months of installation.
- 6 - The percentage knockdown and mortality at 24 hours of ITENs and ITWs after 12 months of
7 installation.
- 8 - The percentage chemical content of ITENs and ITWs after 12 months of installation.
- 9 - The percentage acceptance of ITENs and ITWS in the community using the structured
10 questionnaire.
- 11 - The behaviour, practice and use of ITENs and ITWS in the community from FGDs.

12

13

14

15

16

17

18

19

20

21

1 **Participant timeline {13}**

	STUDY PERIOD							
	Enrolment	Allocation	Post allocation					Closeout
TIMEPOINT	May	June, 2021	Aug 2021	Dec, 2021	Jan, 2022	June, 2022	July, 2022	Sept, 22
Eligibility screen/ baseline data	X							
Informed consent / Allocation	X							
Installation in the intervention arm		X						
Installation in the control arm								X
ASSESSMENTS								
Perceived adverse effect			X					

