50 ul blood from members of above 6 months old					X	X		
Density of malaria vectors and Nuisance mosquitoes					X	X		
Feasibility Cost		X						
Longevity, fabric integrity, community acceptance and practice.				X		X		
Bioefficacy & Chemical retainment						X		

2

3

4 **Sample size {14}**

5 With 225 houses per arm was an assumed 4.5 residents per household (14), then if prevalence in
6 the control arm is 20% the study would have 90% power to detect a relative reduction of 30% to a
7 prevalence of 14% assuming a conservative between-house coefficient of variation of 0.5.

1

2 **Recruitment {15}**

3 Once permission from the District Medical Officer and village heads is obtained, meetings with
4 the village leaders will be convened to discuss the aim and procedures of the trial, and to select the
5 villages where houses that meet eligibility criteria can be found. Once villages are selected,
6 community sensitization will be conducted among all the selected villages to provide information
7 on the purpose of the study to the people, including the adverse consequences of vector-borne
8 diseases, the benefits and risks of using ITENS and ITWS, and caring for the intervention. This
9 will be followed by recruitment of the households through door-to-door process, facilitated by
10 community leaders as key informants to introduce field teams to households.

11

12 **Assignment of interventions: allocation**

13 **Sequence generation {16a}**

14 Household identification numbers stratified by sub-village will be provided to a statistician that
15 will not be in the field during the community enrolment. Simple randomization within blocks of
16 sub-villages to randomly allocate households between two arms will be conducted. Randomization
17 of all study households will be done simultaneously.

18

19 **Concealment mechanism {16b}**

20 This trial will not have continuous recruitment. All households will be recruited at the start of the
21 study and randomized simultaneously.

1

2 **Implementation {16c}**

3 After enrollment of all households by trained field workers, the trial statisticians will generate
4 allocation sequence and assign households to interventions through randomization stratified by
5 sub-village.

6

7 **Assignment of interventions: Blinding**

8 **Who will be blinded {17a}**

9 This is an open label trial because intervention can be visually observed.

10

11 **Procedure for unblinding if needed {17b}**

12 Not Applicable.

13

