14 **Data collection and management**

15 **Plans for assessment and collection of outcomes {18a}**

16 Quantitative data such as malaria prevalence, clinical malaria cases, mosquito density, feasibility,
17 cost, adverse effects, attrition, integrity and use practice of the tool will be entered using Open
18 Data Kit (ODK) (15) installed on android tablet computers. Paper data forms will be available to
19 the field team for use in the eventuality of tablet computer failure. Data collected will be uploaded
20 to the IHI secure data repository for data analysis as per the requirement. Qualitative data will be

1 audio recorded (16). Interviews will be saved in an external hard-drive and locked in a secure file
2 cabinet. Mosquitoes will be collected using CDC light traps to measure the effect of the
3 intervention on the density of malaria vectors and nuisance mosquitoes (9). Blood samples will be
4 collected using New MiniCollect® K2EDTA Capillary Tube, manufactured by Greiner Bio-One,
5 Austria. The blood samples will be kept in cool box before they are transferred to the lab for qPCR
6 analysis. To confirm malaria cases, calibrated ear thermometer will be used to record body
7 temperature of those with positive mRDT. The study personnel, field workers/data collectors are
8 trained on correct data input methods to ensure data integrity.

9

10 **Plans to promote participant retention and complete follow-up {18b}**

11 Field interviewers recruited to support data collection will be from the study villages. Phases of
12 data collection will involve door to door surveys, with respective sub-village heads guiding field
13 interviewers to households, as participants are more likely to stay in the trial when familiar faces
14 are involved. Achieving complete follow-up in village settings may also be influenced by time of
15 data collection, as most of the study village residents are farmers and are more likely to be in their
16 farms throughout the daytime during cultivation and harvesting season, therefore follow up visits
17 for data collection will occur at a time when participants are available e.g. in the early morning or
18 evening. Data collectors will revisit absent households to ensure completeness of data collection.
19 However, in case of discontinuation by the participants, the information that will be recorded are
20 date, data collectors name, house code, GPS location and consent.

21

22 **Data management {19}**

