9 quantitative polymerase chain reaction (qPCR) analysis. Point of care diagnosis for febrile
10 individuals will be SD Bioline Malaria Ag Pf/Pan rapid diagnostic test (RDT) as per Tanzanian
11 guidelines (13).

12 Used RDT kits will be stored in a locked shipping container at IHI until the data is completed and
13 locked, then the samples will be destroyed on-site in the Clinical Trials facility Incinerator.

14

15 **Statistical methods**

16 **Statistical methods for primary and secondary outcomes {20a}**

17 The primary endpoint which is detection of malaria parasitemia through qPCR after the long rainy
18 season (June/July 2022) will be analysed using mixed effects binary logistic regression, with a
19 random effect for household to account for clustering. Analysis of secondary endpoints malaria
20 parasitemia will be tested using qPCR after the short rainy season (January/February 2022) as well

1 as clinical malaria cases and malaria prevalence shortly after the short rainy season and long rainy
2 will also be analysed following the same approach.

3 Negative binomial mixed effect model will be performed for mosquito density data, with random
4 effect for household.

5 The baseline characteristics collected during the survey, including age, sex, education, number of
6 participants, household size, occupation, sleeping spaces, nets per house, nature of houses (wall,
7 roof, and floor), community acceptance of LLINs (use rate and any side effects) and
8 socioeconomic quintiles will be presented by arm.

9 Principal component analysis (PCA) will be carried out to determine a combination of variables
10 for socioeconomic status to explain the overall observed variation and reduce the complexity of
11 the data, by calculating a weighted score for the socioeconomic status of each household of the
12 population and divided into five quintiles: lowest, low, middle, high and highest.

13 Proportion of the outcomes (attrition, fabric integrity and community acceptance) will be presented
14 in percentages.

15 Recorded information during the FGD will be transcribed and grouped into different themes based
16 on inductive thematic analysis of interview summaries. Reports will be illustrated with verbatim
17 quotes of themes and sub-themes identified.

18

19 **Interim analyses {21b}**

20 No interim analyses will be carried out.

21

1 **Methods for additional analyses (e.g. subgroup analyses) {20b}**

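### The mosquito density model has no term for trapping night and nothing ties trap nights across arms, which costs precision and leaves a timing difference between arms unguarded

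*Protocol*

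**What the plan says.** Statistical methods {20a} gives the whole mosquito analysis in one sentence: "Negative binomial mixed effect model will be performed for mosquito density data, with random" "effect for household". Household is the only random effect named. No term for night, date or sub-village appears.

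Outcomes {12} lists vector and nuisance mosquito density as a secondary outcome in houses with the nets "installed in comparison to the houses without after the short (January/February 2022) and long" rains. On collection, {18a} says "Mosquitoes will be collected using CDC light traps to measure the effect of the" intervention on density. It does not give the number of nights per house, the order of houses, or whether the arms share nights.

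Trial design {8} has 450 households surveyed twice, with light-trap density among the survey measurements. The Participant timeline {13} marks density under January and June 2022. Study setting {9} describes "long rainfall from March to May and short rainfall from November to December", so both surveys follow the end of rain. Sequence generation {16a} specifies "Simple randomization within blocks of" sub-villages. That stratifies by place and does nothing about calendar night. The trial is open label {17a}.

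**The concern.** Light-trap catches vary from night to night with weather, and over weeks as the season moves on. All houses trapped on one night share that variation, so their catches are correlated. A household effect does not describe this correlation, because it groups catches by house and not by date.

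Two consequences follow. First, variation that a night term could remove stays in the error. Second, the validity of the stated standard error depends on how the arms are spread over nights, and the protocol leaves that open. If the arms are balanced on each night, the night effects largely cancel from the comparison. If they are not, part of the night variation enters the arm contrast and the model does not count it.

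Density is the trial's entomological evidence, and the Introduction rests partly on a pilot that reported a 75% reduction in vector density. Scheduling also has to be settled in advance: if the arms share no nights, a night term cannot rescue the comparison.

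**Working it through.** **The plan's own figure.** The protocol gives no power or precision figure for mosquito density. Its only power figure is for qPCR prevalence in {14}, and it reproduces. Houses per arm = (1.96 + 1.2816)² × [0.20×0.80/4.5 + 0.14×0.86/4.5 + 0.5²×(0.20² + 0.14²)] / 0.06² = 10.507 × 0.07721 / 0.0036 = 225.4, against 225 planned (two-sided 5% assumed). It does not bear on the mosquito model.

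**Assumed inputs.** From the protocol: 450 houses, 225 per arm. Not in the protocol, and therefore assumed: one catch per house per survey, 30 trapping nights (450/30 = 15 houses per night), a control mean of 2 per trap night, and a between-night SD *s* of log density of 0.3, 0.5 or 0.8.

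**Step 1: precision.** The variance cut from adding night is 1 − (SD with night / SD without night)², using the empirical SD of the log ratio.

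| *s* | Set A: without / with | Cut | Set B: without / with | Cut |
|---|---|---|---|---|
| 0.3 | 0.133 / 0.131 | 3% | 0.136 / 0.139 | none |
| 0.5 | 0.143 / 0.137 | 8% | 0.169 / 0.158 | 13% |
| 0.8 | 0.174 / 0.134 | 41% | 0.186 / 0.151 | 34% |

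Set A: rate ratio 0.5, dispersion 1, 150 runs. Set B: rate ratio 0.7, negative binomial shape 0.6, both arms on every night, 200 runs. A third set gave roughly nothing, 6-18% and 33-38%. In Set B, power rose from 72%, 65% and 55% to 76%, 69% and 68%.

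An SD estimated from R runs has a relative error of about 1/√(2R): 5.8% at 150 runs and 5.0% at 200. The 0.3 row therefore cannot be told from zero, and the 0.5 row is loose. The 0.8 row is clear.

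**Step 2: is the stated standard error right without a night term?** Null ratio, shape 0.6, 600 runs per setting. The Monte Carlo error of a 5% rate is √(0.05×0.95/600) = 0.9 points.

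| *s* | Arms balanced each night: type I error | Arms at random over nights: empirical SE / model SE | Type I error |
|---|---|---|---|
| 0.3 | 3.3% | 0.150 / 0.142 | 7.0% |
| 0.5 | 5.5% | 0.153 / 0.148 | 5.2% |
| 0.8 | 6.3% | 0.190 / 0.159 | 11.0% |

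The third set gave about 4%, 7% and 11% for random nights, and nominal or below when balanced.

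An approximation explains the gap. If w1 and w0 are the shares of each arm's catches falling on a given night, imbalance adds about (e^(s²) − 1) × Σ(w1 − w0)² to the variance. For random nights, Σ(w1 − w0)² is about 2 × (29/30)/225 = 0.0086. At *s* = 0.8 the added variance is 0.896 × 0.0086 = 0.0077. The simulated difference between random and balanced is 0.190² − 0.169² = 0.0075. At 0.5 and 0.3 the term is 0.0024 and 0.0008, within simulation noise. Balancing arms on each night makes the sum zero.

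**Step 3: what a timing difference would do.** If density falls by a fraction *f* per week and intervention houses are trapped *L* weeks later, a true ratio of 1 appears as (1 − f)^L. For *f* = 0.10, 0.20 and 0.30 this is 0.90, 0.80 and 0.70 at one week, and 0.81, 0.64 and 0.49 at two weeks. Both *f* and *L* are assumed. The protocol supplies neither.

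**The case against.** The strongest reply has four parts.

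- **This is analysis-plan detail.** The protocol refers to a statistical analysis plan that is not shown, and further terms could be added there. This stands in part. However, {20a} does name the random-effect structure, and trap scheduling is a matter for {18a}.
- **The timing bias is conjecture.** A reader might infer that the density ratio will be biased, because the row "Longevity, fabric integrity, community acceptance and practice" and the netting tests fall in June 2022 alongside trapping, concern only houses with nets, and are assigned to the same technicians as the traps. The documents do not support that conclusion. Nothing says these tasks move trap nights, and for the first survey the inspection is in December and trapping in January. Door-to-door work guided by sub-village heads may well mix the arms. With nights falling at random, the ratio is unbiased on average. Type I error of 14%, 24% and 44% at the three night SDs arises only if the arms share no nights, which nothing implies.
- **The trapping period may be short.** {12} allows January/February and June/July, but the timeline marks only January and June. A two-month window should not be assumed. One month is enough for the 30 nights used here.
- **The gain is small unless nights vary a lot.** This stands. At SD 0.3 there is little to gain, and with balanced nights the stated model keeps its type I error.

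A reader might also infer that the household effect cannot be separated from the negative binomial dispersion. That would need one catch per house in each analysed survey, which the protocol does not state.

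**Conclusion.** The point holds in a limited form. The stated mosquito model omits the correlation among catches on one night, and no section ties trap nights across arms. The cost is precision: little at a between-night log SD of 0.3, about 6-18% of the variance at 0.5 and about 33-41% at 0.8. If arms are not balanced over nights, the standard error can also be modestly too small, with type I error of about 4-7% at SD 0.3, 5-7% at 0.5 and 11% at 0.8. These sizes rest on one catch per house, 30 nights and assumed night variation. With more nights per house or fewer houses trapped they would differ.

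A shift of the density ratio through different trap dates is a risk that the plan does not close. It is not a bias that the plan can be shown to create. Only the secondary density outcomes are touched. The primary qPCR endpoint and its sample size are unaffected. The change is worth making because it is cheap and the scheduling part cannot be repaired afterwards.

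**What to change.** In {18a}: on each trapping night, set traps in intervention and control houses of the same sub-village, in as near equal numbers as the allocation allows, and record the trap date with every catch. Exact equality cannot be required, because simple randomization within a sub-village need not give equal arms.

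In {20a}: add a random effect for trapping night, or for sub-village by night, to the negative binomial model. Keep the household effect where houses have repeated catches. The two surveys can still be analysed separately; pooling them is not needed for this.

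The cost is a trapping roster that mixes arms, slightly more field scheduling, one more variance term to estimate, and a sentence in each section. By the Trial status section and the timeline, trapping had not begun at protocol version 6 (November 2021), so the roster could still be set.

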The primary objective of the trial is to investigate the efficacy of ITENs with ITWS on malaria parasite prevalence among residents aged 6 months and above, measured by quantitative polymerase chain reaction (qPCR) shortly after long rainy season (June/July 2022), and after the short rainy season (January 2022) as a secondary outcome. Other secondary objectives are to estimate the effect of the interventions on clinical malaria cases, and density of malaria vectors and nuisance (*Culex quinquefasciatus*) mosquitoes after the i) short rainy season (January/February 2022) and ii) long rainy season (June/July 2022). The cost (fabric amount and time duration) of installing the intervention, perceived adverse effects after one month of installation, and physical durability and community acceptance of the tool after 6 months and 12 months installation, as well as chemical durability after 12 months of installation.

Trial design {8}

A household randomized superiority trial of households with ITENs and ITWS compared to those without them, among villages in Chalinze district located in Pwani region, Tanzania (Figure 2). Four hundred and fifty households will be randomly allocated equally into two arms, and will be surveyed twice in the subsequent year: short rainy season (January/February 2022) and long rainy season (June/July 2022). The surveys will assess the malaria prevalence of all participants using quantitative Polymerase Chain Reaction (qPCR) (8); clinical malaria cases defined by fever and malaria rapid diagnostic test (mRDT), SD Bioline; and the density of malaria vectors and nuisance mosquitoes will be measured using Centres for Disease Control (CDC) light traps (9).

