2 An analysis of the intervention effect within subgroups defined by age (under 5s, aged 5-15, and
3 aged 16 or over), socioeconomic status, gender, among others will be carried out on malaria
4 prevalence at both surveys using the same methods as for the primary endpoint.

5

6 **Methods in analysis to handle protocol non-adherence and any statistical methods to handle**
7 **missing data {20c}**

8 Minimal protocol non-adherence is expected because of the nature of the intervention, however
9 we will carry out an intention to treat in which households are analysed according to allocation
10 regardless of whether the intervention was adhered to. A secondary per protocol analysis which
11 excludes houses that removed the intervention will be carried out. At an individual level,
12 participants who report being away from home for more than a week during the fortnight preceding
13 testing will be excluded from the primary analysis but included in a secondary analysis. We expect
14 there to be minimal missing data on the primary endpoint, in which case complete case analysis
15 will be used. If there is more missing data than expected, a secondary analysis in which multiple
16 imputation is applied under the assumption of missing at random will be carried out.

17

18 **Plans to give access to the full protocol, participant level-data and statistical code {31c}**

19 Full protocol, statistical analysis plan, anonymized level-data and statistical code will be made
20 available on reasonable request.

21

1 **Oversight and monitoring**

2 **Composition of the coordinating centre and trial steering committee {5d}**

3 The Ifakara Health Institute is the trial sponsor and coordinating centre. Study investigators meet
4 weekly to review trial progress. A trial steering committee consisting of study investigators and
5 independent experts will meet after every study survey.

6

7 **Composition of the data monitoring committee, its role and reporting structure {21a}**

8 Although we don't anticipate any safety issues in this trial since the intervention is similar to LLINs
9 which are used extensively in malaria endemic regions a data monitoring committee has been
10 appointed. The committee is composed of a clinician, an entomologist and a statistician, is
11 independent of the trial sponsor and funder, and has no competing interests. The committee will
12 meet after the data from each survey have been collected. The committee will consider safety data

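### The secondary per-protocol analysis can drop houses from the intervention arm only, without adjustment, so it can be biased in either direction if net removal is related to malaria risk.

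*Protocol*

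**What the plan says.** Protocol section {20c} opens with "Minimal protocol non-adherence is expected because of the nature of the intervention, however" and then commits to analysing households as allocated, whatever their adherence. It adds one further household-level analysis, introduced as "A secondary per protocol analysis which" and completed by "excludes houses that removed the intervention will be carried out". It gives no exclusion for control houses and no adjustment for differences between houses that kept the nets and houses that removed them.

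Three other places bear on this rule:

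- Section {11b} gives two routes to removal, both decided by participants after allocation: withdrawal, with the option of having the nets taken down, and removal on request because of perceived adverse effects.
- Section {11c}, section {30} and the timeline in {13} put installation in the control houses at the end of the trial (September 2022).
- Section {12} lists as a secondary outcome "The physical presence and numbers of holes visually observed in ITENs and ITWs after 6" and 12 months. The abstract places these surveys in the houses that received the intervention.

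**The concern.** A control house has no trial nets to remove until after the primary endpoint, so the rule can act on one arm only. The houses left in the intervention arm have in effect chosen to stay, while the control arm still contains houses that would have removed the nets if given them. If the choice is related to malaria risk, the two groups differ for a reason other than the nets.

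What is at stake is the reading of a secondary result. A gap between the per-protocol and intention-to-treat estimates could be taken as the effect of keeping the nets up, when part or all of it could be selection. The distortion grows with the share removed, so the analysis is least reliable when non-adherence is large enough for someone to want it.

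**Working it through.** **Design figure first.** Section {14} states "With 225 houses per arm was an assumed 4.5 residents per household (14), then if prevalence in" "the control arm is 20% the study would have 90% power to detect a relative reduction of 30% to a" "prevalence of 14% assuming a conservative between-house coefficient of variation of 0.5". Section {8} gives equal allocation: "Four hundred and fifty households will be randomly allocated equally into two arms". I assume a two-sided 5% test, since section {14} states no significance level.

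- Variance of a house-level prevalence: p(1−p)/m + (CV × p)², with m = 4.5 and CV = 0.5.
- Control: 0.20 × 0.80/4.5 + 0.10² = 0.04556.
- Intervention: 0.14 × 0.86/4.5 + 0.07² = 0.03166.
- Standard error: √[(0.04556 + 0.03166)/225] = 0.01852.
- Power: Φ(0.06/0.01852 − 1.96) = Φ(1.28) = 89.9%.

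The stated 90% is reproduced, so the same house-level test can be used to gauge the exclusion rule.

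**Bias of the exclusion analysis when the nets do nothing.** Let r be the share of intervention houses that removed the nets, and k their prevalence relative to the remaining intervention houses. With no effect, the whole intervention arm has the control prevalence p. If the remaining houses have prevalence q, then p = (1−r)q + r·k·q, so

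per-protocol prevalence ratio q/p = 1/(1 − r + r·k).

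Both r and k are assumptions; the protocol gives neither.

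| r | k = 0.5 | k = 1 | k = 1.5 | k = 2 |
|---|---|---|---|---|
| 5% | 1.03 | 1.00 | 0.98 | 0.95 |
| 10% | 1.05 | 1.00 | 0.95 | 0.91 |
| 20% | 1.11 | 1.00 | 0.91 | 0.83 |

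Example: r = 0.10 and k = 2 give 1/(0.90 + 0.20) = 0.909. With r = 0.10 and k = 0.5, 1/(0.90 + 0.05) = 1.053.

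**Chance of a falsely significant protective result.** The nominal figure is 2.5%. Take p = 0.20, 225 control houses and 225(1−r) intervention houses. For r = 0.10 and k = 2:

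- q = 0.20 × 0.909 = 0.1818.
- Variance of an intervention house: 0.1818 × 0.8182/4.5 + (0.5 × 0.1818)² = 0.04132.
- Standard error: √(0.04556/225 + 0.04132/202.5) = 0.02016.
- Shift: (0.20 − 0.1818)/0.02016 = 0.90.
- Chance: Φ(0.90 − 1.96) = 14.5%.

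| r | k = 0.5 | k = 1 | k = 1.5 | k = 2 |
|---|---|---|---|---|
| 5% | 1.4% | 2.5% | 4.3% | 6.9% |
| 10% | 0.7% | 2.5% | 6.8% | 14.5% |
| 20% | 0.2% | 2.5% | 13.9% | 37.5% |

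These percentages come from a house-level normal test, not the planned mixed logistic model, so they are approximate. They also depend on how k is defined: twice the mean of the whole arm is stronger selection than twice the prevalence of the remaining houses.

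**Complier-average estimate on the same inputs.** Before closeout no control house has trial nets, so non-adherence is one-sided and the complier-average risk difference is the intention-to-treat difference divided by (1−r). With no effect this is 0/(1−r) = 0, whatever k is. At the design difference of 6 percentage points it would be 6/0.95 = 6.3 points at 5% removal and 6/0.90 = 6.7 points at 10%.

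**The case against.** The strongest reply is that the rule does little harm. The analysis is labelled secondary, in a superiority trial that also analyses houses as allocated, so the rule cannot change the intention-to-treat result. The protocol expects minimal non-adherence because the netting is hardwearing. At an assumed 5% removal the spurious ratio is 0.98 to 0.95, against a design ratio of 0.14/0.20 = 0.70. Details of a secondary adherence analysis are also often left to the statistical analysis plan, which is not shown. All of this limits the importance of the point. It does not remove it: the exclusion rule itself is fixed in the protocol, and it is the rule that breaks the randomised comparison.

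A reader might infer that the per-protocol analysis will favour the nets. The documents do not support that. They say nothing about whether houses that remove nets have higher or lower malaria risk. If removal is unrelated to risk there is no bias at any removal rate, and if removers are at lower risk the bias runs against the intervention. Nor do they give any basis for expecting 10% or 20% removal.

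A reader might also want control houses that screen their own windows or close their eaves to be counted as non-adherent. That would not support a charge of spurious protection, because such houses dilute the contrast toward no effect. The protocol also plans no follow-up record of screening in control houses, so this is not part of the point.

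**Conclusion.** The point holds in a limited form. The per-protocol rule excludes self-selected houses, can do so in one arm only, and states no adjustment. Its estimate is therefore not protected by randomisation and can be biased toward or away from a protective effect. At the low removal that the protocol expects, the bias is small to modest. It becomes material only if about 10% or more of intervention houses remove the nets and those houses differ clearly in risk. This rests on assumed values of r and k and on a house-level approximation to the planned model. It is a worthwhile improvement to a secondary analysis and does not threaten the trial's main conclusion.

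**What to change.** In section {20c}:

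1. Label the exclusion analysis as supportive.
2. Report how many intervention houses were excluded, with their baseline characteristics beside those of the houses that stayed in.
3. Adjust the exclusion analysis for the baseline house and socioeconomic variables that section {20a} already lists.
4. Add a complier-average estimate with allocation as the instrument and, as exposure, the net presence already recorded in intervention houses at 6 and 12 months.

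The cost is wording and one further model, with no new data collection. Protocol version 6 (4 November 2021) precedes the January 2022 prevalence survey, so at that version the change could be made before any prevalence outcome was seen. The drawbacks are a wider interval and the usual instrument assumptions. One of these is strained here: houses that removed the nets late had partial protection, so treating them as unexposed is not exact. Adjustment in step 3 reduces bias only as far as the recorded variables explain who removes the nets.
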